# 6.2.10 Open-Label Study Segment for Low Dose and Medium Dosage Participants ("Stage 2")

Participants assigned to receive low dose or medium dose MDMA during Stage 1 will undergo three open-label MDMA-assisted psychotherapy sessions that follow a course and schedule similar to Stage 1 for the full dose group except that participants will

undergo one instead of three introductory sessions. After confirming consent and eligibility criteria, participants continuing to Stage 2 will meet with both investigators conducting psychotherapy for a single review and preparatory psychotherapy session before the first open-label MDMA-assisted psychotherapy session. If more than 8 weeks have passed since the primary endpoint, all measures will be repeated for a new baseline prior to the first open-label experimental session. Experimental sessions will be conducted according to procedures described in Section 6.2.3. During the first experimental session, subjects will receive a 100 mg initial dose of MDMA and may receive a 50mg optional supplemental dose of MDMA. At the beginning of each of the second and third experimental sessions, the co-therapists, in consultation with the subject, will decide whether to administer an initial dose of 100 mg or 125 mg initial dose of MDMA. If a 100mg initial dose of MDMA is selected, an optional supplemental dose of 50mg MDMA may be administered. If a 125mg initial dose of MDMA is selected, an optional supplemental dose of 62.5mg MDMA may be administered. If the PI decides not to administer the optional supplemental dose and/or the optional clinical titration dose in a given experimental session, the unused capsules will be kept in their respective inner envelopes inside of the primary container in the safe.

Integrative sessions will be conducted according to procedures described in Sections 6.2.4 and 6.2.6. Phone calls will be conducted according to procedures described in Section 6.2.5.At the secondary endpoint based on procedures described in Section 6.2.7, the Independent Rater will administer the CAPS and GAF. Subjects will complete the BDI-II, PSQI, PTGI (in reference to the start of the study), and DES-II.Administration of the CAPS may be recorded to video.

Investigators will follow the most recent treatment manual in all matters relating to the Open-Label Stage 2 experimental psychotherapy sessions

Spontaneously reported reactions, SAEs, AEs and medications will be collected and reported in the same manner as during Stage 1. The visual analog scale will be used to collect changes in subjects who have pre-existing tinnitus and chronic pain symptoms as in Stage 1.

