The 100mg MDMA initial dose will be administered in the first experimental session in Stage 2 to enable a comparison of subjective and therapeutic effects to full dose MDMA. Prior to both the second and 3rd experimental sessions in Stage 2 the co-therapists, in consultation with the subject, will decide whether the same dose or an initial dose of 125mg (each with the corresponding optional supplemental dose) would be more likely to constitute the optimal therapeutic dose for each of these experimental sessions.

MDMA in bulk will be sent from Organix Inc., in Woburn, MA, to the Clinical Investigator, who has been issued the Schedule 1 license by the Drug Enforcement Agency (DEA). The Clinical Investigator and unblinded Randomization Monitor will oversee compounding by a pharmacist in a manner that will maintain the blind for the Clinical Investigator. The pharmacist will provide bulk lactose for compounding MDMA capsules. The pharmacist will weigh the MDMA into doses of 125, 100, 75, 62.5, 50, 37.5, 30, 25 and 12.5 mg (calculated as the weight of the hydrochloride salt) and placed in gelatin capsules in combination with lactose used to ensure that all blinded capsules have similar appearance and weight. Capsules for the initial dose will be a different color from capsules used for the supplemental dose. All capsules will be compounded so that they weigh the same amount, but contain varying amounts of MDMA and lactose. Capsules for all experimental, triple-blind sessions will be prepared in such a way as to prevent Clinical Investigators and subjects from distinguishing contents of blinded capsules. Dosage for open-label sessions will be clearly indicated in the packaging.

Doses of MDMA for each experimental session will be stored in separate primary containers labeled with the protocol number, drug name, lot number, unique container number, sponsor name and a statement that the drug is for clinical trial use only. Labels for each container of MDMA will be provided by the sponsor and applied by the pharmacist. The contents of the blinded primary containers will be hidden from the investigator to assure blinding.

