A co-therapist team will perform all non-drug and MDMA-assisted psychotherapy sessions in their outpatient office. Participants will complete the SOCQ, a measure of alterations in consciousness related to mystical experiences, during the period of time between the end of each MDMA-assisted psychotherapy session and before they leave the treatment facility the next day. Participants will remain at the study site overnight accompanied by an attendant. Participants will undergo three integrative psychotherapy sessions after each experimental session, with the first integrative session occurring on the day after the experimental session.

A blinded independent rater, who will not be present during any psychotherapy sessions, will assess participant PTSD symptoms with CAPS, symptoms of depression with BDI-II, posttraumatic growth with PTGI, global functioning with GAF, sleep quality with PSQI, and dissociation with the DES-II. Changes in personality traits will be assessed via NEO-PI. Outcome assessments will be done at baseline, at the primary endpoint one month after the second experimental session, two months after the third open-label experimental session and at the 12-month follow-up and at equivalent points in Stage 2.

When each subject completes the evaluation at the primary endpoint, the blind will be broken for that subject. Participants who had been assigned to receive low dose or medium dose MDMA will subsequently have the opportunity to enroll in the open-label study arm, or "Stage 2." Stage 2 must start within a maximum of 5 months after the participant finishes Stage 1. The open-label study arm will follow a similar sequence of events and procedures, except that there will be a single preparatory session, and all three MDMA-assisted psychotherapy sessions will be open-label. Subjects will receive an initial dose of 100 mg MDMA in the first experimental session, and one of two active doses of MDMA that are clinically titrated by the CI during the second and third open-label experimental sessions that will otherwise follow the same sequence of events (See Time and Events Table). Outcome measures except for the NEO PI will be repeated one month after the second Stage 2 experimental session, and all outcome measures will be repeated at the end of Stage 2.

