#### **6.1 Assessments and Measures**

The following outcome and safety measures will be employed in Stage 1 and Stage 2, following a similar sequence of events to the full dose subject group in Stage 1, except that participants in Stage 2 will have one and not three preparatory (introductory) sessions.

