# 6.2.3 MDMA Sessions [Visits 5, 9, and 14 (Visit 14 for full dose group only)]

Subjects in Stage 1 will receive two experimental sessions of MDMA-assisted psychotherapy blinded with respect to dose, scheduled approximately 3-5 weeks apart. Subjects in the open label third experimental session in Stage 1 will receive experimental sessions with the full dose of MDMA.

Each experimental session will last approximately eight hours followed by an overnight stay at the study site. Experimental sessions will be conducted by the male and female cotherapist team. Procedures for MDMA-assisted psychotherapy will remain the same across all sessions, and all procedures except drug dose will be the same for participants assigned to the full, medium and low dose conditions.

Adherence criteria for experimental sessions should be completed as a part of each experimental session. These elements do not have to be accomplished in any specific order. Generally, adherence criteria for these sessions include that the therapists will

create and communicate a setting of safety and support the subject during periods of inner focus. Therapists will use a largely nondirective approach, following the lead of the subject's inner healing intelligence. Therapists will provide encouragement for staying present with difficult experiences. Therapists may occasionally offer gentle guidance or redirection as a choice to encourage collaborative exploration if the subject repeatedly avoids trauma related material. Therapists will inquire about somatic symptoms and if necessary encourage release of tension through movement, in whatever way feels appropriate to the subject. Therapists will use music to support the experience without being intrusive.

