Blood pressure and pulse will be measured at the outset of the experimental session, once every 15 minutes for the first 4 hours of the MDMA-assisted session and every 30 minutes for another 2 hours. More frequent measures will be taken as described in section 6.1.2 if the established thresholds are exceeded, or if the subject has a diagnosis of hypertension. For subjects without a diagnosis of controlled hypertension, after viewing baseline values at the beginning of the session, the investigators will only view the blood pressure or pulse values in the case of a medical indication in order to improve the effectiveness of condition blinding. More frequent measures will be taken if the participant exhibits symptoms that could be related to hypertension, hypotension tachycardia or bradycarida. In the event of any medical indication, such as signs or symptoms that could be related to either hypertension or hypotension, the investigators have the option to print out the results during the session.

Participant body temperature will be measured via tympanic thermometer every 60-90 minutes. Participants will complete the SUD every 90 minutes, until the session is over, allowing a window of plus/minus 30 minutes to fit into the psychotherapy process where a natural break occurs. If necessary, the investigators can make a greater number of SUD measurements as their clinical judgment dictates. The investigators will record any spontaneously reported reactions during the session. If subjects who have pre-existing tinnitus or chronic pain mention any changes, the visual analog scale will be used to collect the changes in symptoms.

A supplemental dose half the size of the initial dose may be administered 1.5 to 2.5 hours after the initial dose upon mutual agreement between the investigators and the participant.

Approximately six hours after drug administration, the investigators will administer the C-SSRS.

If there is a support-individual who has previously been asked and has agreed to be present during part or all of the MDMA session, that person may arrive during the session at whatever time has been agreed upon, but will wait in the waiting room until brought back to the session room by one of the therapists.

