## 6.2.7 Evaluation at Primary Endpoint & Unblinding (Visit 13)

The primary endpoint evaluation in Stage 1 will occur one month after the second blinded experimental session. This visit will consist of two meetings that may be completed on separate days, one with the independent rater and the other with the therapists. The blinded independent rater will administer: CAPS to assess PTSD symptoms, BDI-II to assess depression symptoms, GAF to assess general psychological function, PTGI to assess post-traumatic growth (in reference to start of the study), PSQI to assess sleep quality, DES-II to assess dissociation symptoms and NEO PI to assess personality. The blinded independent rater will provide their belief of the subject's condition assignment.

After completing all assessments and measures with the independent rater, the subject will meet with the therapists for approximately 30 minutes. Following the visit with the independent rater the blind will be broken for the subject's condition assignment. The independent rater will remain blind to condition assignment at this time. The therapists will assess suicidality with the C-SSRS. The visual analog scale will be used to collect

changes in subjects who have pre-existing tinnitus and chronic pain symptoms.

If the subject had been assigned to receive medium dose or low dose MDMA, the therapists will discuss continuation to Stage 2. Low and medium dose subjects will not complete the third experimental session and associated integrative sessions in Stage 1. Participants who decline continuing to Stage 2 will complete the Responses to Research Participation Questionnaire (RRPQ). If participants had been assigned to the full dose condition in Stage I, they will provide their perceptions of experimental sessions at this point. The therapists will discuss scheduling the third open label full dose experimental session and integrative sessions.

Adverse Events and medications will be collected as described in Sections 8 and 9 of the protocol.

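### Read literally, the blinding-motivated limit on viewing blood pressure and pulse also covers the open-label sessions V14, V20, V24 and V29, where there is no blind left for it to protect

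*Protocol*

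**What the plan says.** **The rule.** Protocol 6.2.3 says that, for subjects not diagnosed with controlled hypertension, the investigators see the baseline values and from then on will only "view the blood pressure or pulse values in the case of a medical indication in order to improve the effectiveness of condition blinding". Section 6.1.2 states the same rule with the same reason. It adds that the night attendant prints the readings after the session and seals them until that subject has been unblinded. For subjects with controlled hypertension, 6.1.2 has the investigators view each reading as it is taken.

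**Where the rule applies.** The heading of 6.2.3 reads "MDMA Sessions [Visits 5, 9, and 14 (Visit 14 for full dose group only)]". V14 is the open-label third session of the full-dose group. Section 6.1 opens with "The following outcome and safety measures will be employed in Stage 1 and Stage 2". For Stage 2 (V20, V24 and V29), 6.2.10 says "Experimental sessions will be conducted according to procedures described in Section 6.2.3" and makes no exception for the viewing rule.

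**When the blind ends.** Section 5.0: "When each subject completes the evaluation at the primary endpoint, the blind will be broken for that subject". That evaluation is V13, before V14 and before all of Stage 2. Section 4.3 adds: "Dosage for open-label sessions will be clearly indicated in the packaging".

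**The concern.** A restriction on looking at safety readings is acceptable when it buys something. At V5 and V9 it helps to keep the therapists from inferring the dose. At V14 and throughout Stage 2 the therapists and the subject already know the dose, and in the second and third Stage 2 sessions the therapists choose it in consultation with the subject. A site following the text to the letter would then withhold routine viewing and gain nothing.

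These sessions all use an active dose: 125 mg at V14, and 100 or 125 mg in Stage 2, each with an optional half-size supplement. Section 7.4.1 expects marked but transient rises at 125 mg followed by 62.5 mg. Its table for the earlier trial shows a mean systolic increase of 28.21 mmHg on MDMA against 13.38 mmHg on placebo, with MDMA readings up to 179 systolic, 113 diastolic and 141 beats per minute. What is at stake is that a rise without symptoms might be noticed later than it need be.

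**Working it through.** **Step 1. Does the text reach the open-label visits?**

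| Visit | Status | Route by which the rule applies |
|---|---|---|
| V5, V9 | Blinded | 6.1.2; 6.2.3 heading |
| V14 | Open-label, full dose | 6.1.2; 6.2.3 heading |
| V20, V24, V29 | Open-label, Stage 2 | 6.1.2 through 6.1; 6.2.3 through 6.2.10 |

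Neither document has a sentence that ends the viewing rule at unblinding. The nearest is the envelope wording in 6.1.2, which governs the printed record and not viewing during the session.

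**Step 2. Is any blind still protected?** The subject and both therapists are unblinded at V13. The independent rater is not; 6.2.7 says "The independent rater will remain blind to condition assignment at this time". But the rule restricts the investigators, and 5.0 and 6.0 keep the rater out of every psychotherapy session. Viewing by the therapists does not in itself tell the rater anything.

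**Step 3. How many sessions fall under the literal text?** The plan gives no total, so there is no figure to reproduce. The inputs are 12 full-dose, 6 medium-dose and 6 low-dose subjects (4.3, 5.2), two blinded sessions each (5.0), one open-label session per full-dose subject (5.0), and three per crossover subject (5.0, 6.2.10). Let k be the number of crossover subjects who complete Stage 2, from 0 to 6 + 6 = 12.

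- Blinded sessions: 24 × 2 = 48
- Open-label sessions: 12 × 1 + 3k
- All sessions: 48 + 12 + 3k = 60 + 3k

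| k | Open-label | All | Share |
|---|---|---|---|
| 0 | 12 | 60 | 20.0% |
| 6 | 30 | 78 | 38.5% |
| 12 | 48 | 96 | 50.0% |

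**Step 4. Exempt subjects.** Subjects with controlled hypertension are viewed in real time already. With *a* such subjects among the full-dose group and *b* among those crossing over, the count is (12 − a) + 3(k − b). The documents give no expected number. As an assumption only, take 0 to 4 in total, split evenly when there are four (a = b = 2):

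- k = 0: from 12 down to 12 − 2 = 10
- k = 12: from 48 down to (12 − 2) + 3 × (12 − 2) = 10 + 30 = 40

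Dropout after V13, which 5.2 and 6.3 do not replace, lowers the count further.

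**The case against.** The strongest reply is that the rule limits itself. It carries its purpose in both places where it appears. In 6.1.2 the viewing limit and the sealed envelope are consecutive steps of one arrangement, and the sealing ends at unblinding. Read by its purpose, the rule has no work to do at V14 or in Stage 2, and the number of affected sessions is zero. The cross-references in 6.2.10 also cannot all be taken literally. They bring in 6.2.4 and 6.2.7 as well, which contain guesses of assignment and the breaking of the blind, and the Stage 2 schedule has no row for either. This reply largely stands. It makes a drafting carry-over the likely explanation. It does not put the limit on the page, and site staff should not have to infer when a restriction on safety monitoring ends.

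Two arguments that might seem to strengthen the literal reading do not:

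- Section 6.1.3 confines the belief-of-assignment measure to blinded sessions, and a reader might infer that silence on the viewing rule is deliberate. But 6.2.4 states the belief step without that limit under a heading that includes the open-label Visit 15, and the Stage 1 schedule marks it there. Silence in the visit sections shows little about intent.
- Section 6.2.3 says "Procedures for MDMA-assisted psychotherapy will remain the same across all sessions". That sentence is about psychotherapy procedures and goes on to comparability between dose groups. It does not settle when readings may be viewed.

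There are also real mitigations. Readings are taken and recorded on schedule, the investigators are present, and they may look whenever there is a medical indication. Section 7.4.1 puts pressures above 140/90 at about 5% of participants per trial, none needing intervention, and reports no rise after the supplement beyond that after the initial dose. By V14 a full-dose subject has had two earlier sessions at that dose, and those readings can be opened. This last point does not help Stage 2 subjects moving up from 30 or 75 mg.

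**Conclusion.** The point holds as a correction to an over-broad rule: read literally, 6.1.2, 6.2.3 and 6.2.10 keep the viewing limit in force at V14, V20, V24 and V29 after its only stated reason has ended. It is minor.

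The size is up to 12 + 3k planned sessions, that is 12 to 48, before removing controlled-hypertension subjects and dropouts. This counts sessions under the literal text; it is not an estimate of sessions in which viewing would in fact be withheld. The 48 assumes that all twelve eligible subjects cross over and complete Stage 2.

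A reader might infer that subjects go unmonitored, or that a safety flaw has been shown. The documents support neither: measurement continues, viewing on indication is always open, and the harm cannot be quantified and is probably small. A reader might also add the thresholds that 6.2.3 attributes to 6.1.2 and that 6.1.2 does not list. That is a separate gap, equally present at V5 and V9, and should carry no weight here.

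No endpoint is affected. The primary endpoint at V13 precedes every session concerned. Viewing might inform the optional supplement in open-label sessions, but the documents do not say so, and the Stage 2 to Stage 1 comparisons already differ in dose and blinding.

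**What to change.** In 6.1.2 and 6.2.3, state that the viewing restriction applies only to the blinded sessions V5 and V9, and that at V14, V20, V24 and V29 the investigators view blood pressure and pulse as they are measured, as 6.1.2 already provides for subjects with controlled hypertension. Put a cross-reference in 6.2.10. The envelope rule needs no change, because sealing already ends at unblinding.

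The cost is one sentence in each of two sections and one cross-reference. No measurement is added, since the automatic cuff already takes the readings on the same schedule. No blinding is lost, because the subject and the therapists already know the dose at these visits.

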# 6.2.11 Assessment Two Months after Third Open-Label Session (End of Stage 2)

All participants in Stage 2 will be assessed by the independent rater two months after their final open-label session. At that visit, the independent rater will administer the CAPS, which may be recorded to video, and assess participants on the GAF, and participants will complete the BDI-II, PTGI (in reference to the start of the study), PSQI, DES-II, and NEO-PI. Participants will also complete C-SSRS and RRPQ with the therapists. Participants will provide their perception of the experimental sessions. Adverse Events and medications will be collected as described in Sections 8 and 9 of the protocol. The visual analog scale will be used to collect changes in pre-existing tinnitus and chronic pain symptoms.

Subjects will receive a memory aid card for use between this visit and the 12-month follow up. Subjects will use this card to record AEs, medications, and changes in psychiatric status that they will be asked about at the termination visit. Memory aids will not be collected. Subjects may return to taking psychiatric medications from this point onward if necessary.

### 6.2.12 Evaluation 12 Months after Final Experimental Session

All participants who completed Stage 1 only will be evaluated 12 months after their third experimental session, and all participants who completed Stage 2 will be evaluated 12 months after their third open-label MDMA-assisted psychotherapy session. The independent rater will administer the CAPS and assess participants on GAF, and participants will complete the PTGI (in reference to the start of the study), BDI-II, PSQI, DES-II and NEO PI. Suicidality will be assessed with the C-SSRS. Participants will also complete a questionnaire assessing positive and negative long-term effects of the study. Outcome measures will either be completed over the telephone or at the study site. A researcher who is a part of the study team may ask the subject questions about positive or negative effects about the study in person or on the phone and the participant will return self-report questionnaires in envelopes supplied by the investigators with the study site listed both as the mailing and return address. The visual analog scale will be used to collect changes in subjects who have pre-existing tinnitus and chronic pain symptoms. Subjects will complete the termination visit at this time.

Adverse Events and medications will be collected as described in Sections 8 and 9 of the protocol.

